3.5 If applicable, please select the Designated Department Approval(s)

Add the name of the individual authorized to approve and sign off on this protocol from your Department (e.g. the Department Chair or Dean).

4.0

Initial Screening Questions

Updated June 2017

4.1 * PROJECT SUMMARY: (REQUIRED) Give a brief overview of this project (250 words or less). Tell us what this study is about, who is being studied, and what it aims to achieve. If you have an NIH Abstract, paste it here: Click on the orange question mark to the right for more detailed instructions.

This is a randomized controlled trial (RCT) exploring the effect of using the Livongo Health Diabetes Management Program versus standard blood glucose (BG) monitoring on glycemic control, as measured by change in hemoglobin A1c (A1c), in adults with diabetes over the course of 6 months. Secondary outcomes include frequency of BG monitoring, frequency of BG measurements outside of the target range, change in diabetes distress, and number of self-reported emergency room visits or hospitalizations.

4.2 * HUD DEVICE: (REQUIRED) Does this application involve a Humanitarian Use Device (HUD):

- No
- Yes, and it includes a research component
- Yes, and it involves clinical care ONLY

4.3 * TYPE OF RESEARCH: (Click the Help link for definitions and guidance): (REQUIRED)

- Biomedical research

- Social, behavioral, educational, and/or public policy research
- Hybrid - includes aspects of BOTH types of research (check this option if your research is mainly social/behavioral but also involves specimen collection or blood draws to look at biological measures)

4.4 * SUBJECT CONTACT: (REQUIRED) Does this study involve ANY contact or interactions with participants:

- Yes (including phone, email or web contact)
- No (limited to medical records review, biological specimen analysis, and/or data analysis)

4.5 * RADIATION EXPOSURE: Does your protocol involve any radiation exposure to patients/subjects EITHER from standard care OR for research purposes (e.g., x-rays, CT-scans, DEXA, CT-guided biopsy, radiation therapy, or nuclear medicine including PET, MUGA or bone scans): (REQUIRED)

- Yes No

4.6 * RISK LEVEL: (REQUIRED) What is your estimation of the risk level, including all screening procedures and study activities (Help Text updated 9/13):

- Minimal risk
- Greater than minimal risk

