- Once the baseline A1c value is obtained, the patient will be randomized (block randomization by diabetes type).

3. Device Usage

- After randomization, participants will receive either the Livongo Health system or the iHealth glucose meter by mail.
 - If a participant is randomized to the iHealth treatment group, participants will download the iHealth iOS application (iHealth Gluco-Smart) and receive an iHealth blood glucose meter in the mail. Participants will link the iHealth application with a mobile version of the Eureka mHealth Research Platform.
 - If a participant is randomized to the Livongo system treatment group, the participant will receive the Livongo blood glucose meter device in the mail, create a Livongo account, and link their Livongo account with the Eureka mHealth Research Platform.
- Livongo- or iHealth-specific instructions will be provided with each meter and a study coordinator will be available to answer study participant questions about using the BG meters. Participants may be referred to Livongo or iHealth customer service for technical support, if needed.
- Participants will not be given specific instructions on how often to check their BG, or how often they should use the Livongo system or iHealth glucose meter as a part of this study. This is done in order to determine the uptake of the intervention and resulting behavior without outside prompting.
- Participants will either use the Livongo system or the iHealth glucose meter for 6 months from the time of enrollment in the study.

4. Messaging/Reminders

- Participants who have been mailed a BG meter but are not using the device after two weeks will be contacted by in-app push notifications, text messages, email or a phone call for device setup and/or assistance.
- Participants will also receive reminders to complete study activities via in-app push notifications, text messages, email or a phone call.
- Two weeks prior to the end of the study period, participants will be contacted by email and/or receive in-app push notifications to remind them to complete their A1c measurement and closeout surveys.

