- Other (describe below):

7.14 * SPECIMENS ARE: (check all that apply): (REQUIRED)

- Leftover specimens from a clinical diagnostic or therapeutic procedure
- Specimens collected for research purposes only (including extra samples taken during a clinical procedure)
- Other

7.15 * DESTINATION: Specimens will ultimately be stored (check all that apply): (REQUIRED)

Outside Entity:

- Cooperative group bank
- NIH
- Other university
- Industry sponsor
- Other

UCSF:

- UCSF repository/bank being established under this protocol
- Existing UCSF specimen repository/bank with CHR approval
- Other location at UCSF (please describe)

Provide the name of the bank and iRIS approval number (if not being banked at UCSF under this protocol). If you checked 'Other,' please provide the location or lab:

The blood samples we draw (through Quest Labs or Home Access mail-in kit) will be used for analysis of the participant's blood sugar levels. The study does not intend to store or bank any of the samples after analysis. The participants will be sent their requisition in a secure email or through a secure download link to bring with them to the lab if they miss their selected date.

7.18 * FUTURE SPECIMEN USE: Will any specimens or portions of specimens be retained after the study is over for possible use in future research studies: (REQUIRED)

- Yes
- No

7.20 * CLINICAL FOLLOW-UP DATA: Will clinical follow-up data be linked to specimens (i.e., will medical record information continue to be abstracted after the specimen is collected): (REQUIRED)

- Yes
- No

Provide duration of follow-up or 'indefinitely':

7.25 STATISTICAL METHODS: Briefly summarize the methods and types of analyses that will be performed:

Descriptive statistics (t-tests for continuous variables and chi-squared tests for dichotomous variables) will be used to compare demographic, clinical, and socioeconomic variables. The primary outcome measure is change in A1c. Data will be analyzed as a comparison between experimental and control groups. Data may also be stratified by duration of diabetes and baseline HbA1c (< 7.0% vs 7.0). Methods for analyzing longitudinal data (mixed-effects linear regression models or generalized estimating equations) will be used to look for the effect of using Livongo on change in A1c, adjusting for possible confounding variables. Similar models will be used to examine secondary outcomes.

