Is this a new device or a new use of an already approved device	No
Is an IDE necessary	No
IDE Number	
Who holds the IDE	N/A
IDE details	

In the opinion of the sponsor, select the level of risk associated with this device	No Significant Risk		
 Livongo In Touch Blood Glucose Monitoring System	Yes	No	
Manufacturer/Supplier of Device	Livongo		
Medicare Category	 A  B		
Where will the Devices Be Stored			
Will Devices be supplied at no Cost	Yes		
Is this a HDE (HDE)	No		
HDE Number			
Is the Device FDA Approved	Yes		
Is this a new device or a new use of an already approved device	No		
Is an IDE necessary	No		
IDE Number			
Who holds the IDE	N/A		
IDE details			
In the opinion of the sponsor, select the level of risk associated with this device	No Significant Risk		

8.6 * Is this an expanded access or compassionate use protocol, meaning the primary purpose is to diagnose, monitor or treat a patient's condition, rather than the collection of safety and efficacy data of the experimental agent: (REQUIRED)

Yes No

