- Self-reported A1c level $\geq 7\%$
- Adults, age ≥ 18 years
- Not using continuous glucose monitoring or an insulin pump
- iOS Smartphone with access to data and/or Wi-Fi

9.8 EXCLUSION CRITERIA: List any exclusion criteria (e.g. reasons why someone would not be included in the study):

- Using continuous glucose monitoring during the study period
- People with type 1 DM
- Self-reported A1c level $< 7\%$
- Using an insulin pump during the study period
- Unable or unwilling to switch BG meters to the study meter
- Hospitalization for DKA or hypoglycemia in the past 1 month prior to enrollment
- Pregnant patients, or intention to become pregnant during the study period
- Participants who are currently using, or have ever used, the Livongo Health Program

9.9 * RESEARCH CONDUCTED ON PATIENT CARE WARDS: Do any study activities take place on patient care units at UCSF medical facilities: (REQUIRED)

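### Out-of-range glucose is read on a different meter in each arm, so a between-arm comparison of levels cannot tell a meter difference from a treatment effect

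*Combined protocol and SAP*

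**What the plan says.** - **Outcome.** Section 4.1 includes "frequency of BG measurements outside of the target range" among the secondary outcomes. Section 7.3 names only fasting lipids as secondary.
- **Instruments.** Section 7.9, item 3: "participants will receive either the Livongo Health system or the iHealth glucose meter by mail". Control participants "receive an iHealth blood glucose meter in the mail"; in the other arm, "the participant will receive the Livongo blood glucose meter device in the mail". Section 8.5 lists two devices from two manufacturers, the iHealth system and the "Livongo In Touch Blood Glucose Monitoring System", both marked as FDA approved. It gives no accuracy or agreement figures.
- **Timing.** Section 7.9, item 2: "Once the baseline A1c value is obtained, the patient will be randomized". The meter is mailed after that. Section 9.8 excludes anyone "Unable or unwilling to switch BG meters to the study meter", so the study meter replaces the participant's own.
- **Analysis.** Section 7.25 compares the two arms on change in A1c with mixed models or GEE, adjusted for possible confounders, and then says: "Similar models will be used to examine secondary outcomes". It mentions no agreement check, reference meter, calibration adjustment or sensitivity analysis.
- **Limits.** Readings above 180 or below 80 mg/dL are the cut-offs for the preliminary data in section 7.6. The documents state no target range for the trial itself.

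**The concern.** Meter brand and arm are the same variable. Randomisation balances the people in the two arms but not the instruments, and a meter term cannot be estimated beside an arm term. With no pre-randomisation readings on a common meter, there is nothing from which to estimate an offset and remove it.

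The outcome counts readings beyond fixed limits, so a small proportional offset moves readings across those limits even when true glucose is the same in both arms. At stake is what the trial may conclude about the sponsor's product from this one outcome. The error could run in either direction. Feedback and coaching belong to the intervention, but a reading offset is measurement error and not a change in glycaemia.

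**Working it through.** **The plan's own figures.** None concerns this outcome. The A1c figures in section 9.3 reproduce: n per group = 2 × (1.960 + 0.842)² / (0.5/1)² = 62.8, so 63. With 150 per arm the detectable difference is (1.960 + 0.842) × √(2/150) = 0.323 at 80% power and (1.960 + 1.282) × √(2/150) = 0.374 at 90%, against 0.33 and 0.38 stated. The meter issue does not touch these.

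**Inputs from the documents.** 150 per arm (section 9.1); two-sided 5% test (section 9.3); limits of 80 and 180 mg/dL, borrowed from section 7.6.

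**Assumptions not in the documents.** Readings are lognormal, with between-person CV 20% and within-person CV 25%. Person medians centre on 140 to 180 mg/dL. There is no true difference between arms. The outcome is each person's share of readings out of range, known without reading-level error. One meter reads (1 + b) times the other.

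**Formulas.**
1. For a person with median m: share = Φ([ln 80 − ln m − ln(1+b)]/σ) + 1 − Φ([ln 180 − ln m − ln(1+b)]/σ), with σ = √ln(1 + 0.25²) = 0.246. Average over persons, whose log-medians have SD √ln(1 + 0.20²) = 0.198.
2. d = mean share with the offset minus mean share without it. SE = √[(SD₀² + SD₁²)/150].
3. Chance of p<0.05 = 1 − Φ(1.96 − d/SE) + Φ(−1.96 − d/SE).

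**Worked case, median 165, b = +5%.** The mean share rises from 40.2% to 45.9%, so d = 5.66 points. The person-level SDs are 0.233 and 0.242, so SE = 2.75 points, d/SE = 2.06, and the chance of p<0.05 is 54%.

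**Results** (absolute shift in points; chance of p<0.05; ranges cover offsets in both directions):

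| Person median | Share out of range, no offset | 1% offset | 2% offset | 5% offset |
|---|---|---|---|---|
| 140 | 25% | 0.64–0.67; 6.3% | 1.25–1.37; 10.0–10.4% | 2.85–3.64; 33.9–41.1% |
| 150 | 31% | 0.88–0.90; 6.7% | 1.74–1.83; 12.0–12.1% | 4.16–4.70; 47.5–49.1% |
| 165 | 40% | 1.12–1.13; 7.0% | 2.23–2.26; 13.2–13.4% | 5.51–5.66; 54.1–56.2% |
| 180 | 51% | 1.21–1.22; 7.1% | 2.41–2.45; 13.6–13.9% | 5.95–6.15; 55.4–59.1% |

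**Sensitivity to the model.** Take pooled normal or lognormal readings with mean/SD of 150/50, 170/60 or 190/65 mg/dL. A meter reading 5% low then lowers the out-of-range share by about 3 to 6 points. A 5-point artefact with a between-person SD of 0.25 has SE = 0.25 × √(2/150) = 0.0289, so d/SE = 1.73 and the chance of p<0.05 is 41%. It is 82% at SD 0.15 and 30% at SD 0.30.

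**Change on the same meter.** Apply formula 1 before and after an equal true fall in both arms and take the difference in change. With a 5% offset in either direction, a 5% fall leaves 0.1 to 1.1 points across these medians, and a 10% fall leaves 0.4 to 2.3, against 2.85 to 6.15 in levels. Cancellation is usually substantial but not assured: at median 140 with a 5% low offset and a 10% fall, 2.3 of the 2.85 points remain.

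**The case against.** - **No offset is shown.** This stands. Both meters are listed as FDA approved, and the documents give no bias for either. A reader might infer that the meters disagree, or that the trial will report a false benefit for Livongo. The documents support neither: an offset may be negligible, and it could equally run against Livongo.
- **Longitudinal models can remove it.** This stands in part. A reader might infer that no analysis could help, but that is true only of a comparison of levels. Section 7.25 plans longitudinal models, and section 7.6 analysed change from month one in the preliminary data. A stable offset then largely cancels in most of the cases above. However, section 7.25 does not commit to this form for the secondary outcomes, month one is already on treatment, and a threshold outcome does not cancel exactly.
- **The illustrated size is soft.** This stands. The trial's range is undefined, and frequency could mean a count or a number of days and not a share. Ignoring reading-level error overstates the probabilities for people who test rarely.
- **A strict remedy would amount to a veto.** This stands. At median 165 a 10% upward offset shifts the share by 11.3 points with SE 2.77. A benefit would then have to exceed 11.3 + 1.96 × 2.77 = 16.7 points to survive, and nothing in the documents supports 10% as the bound.
- **Only one secondary outcome is affected.** This stands. A1c and lipids come from Quest or Home Access in both arms, and A1c is already the primary outcome.

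**Conclusion.** The concern holds for a between-arm comparison of levels of out-of-range readings: the plan cannot separate a meter difference from a treatment effect, and it provides no safeguard. Under the stated assumptions, a relative offset of 1%, 2% or 5% produces about 1, 1–2 or 3–6 points of spurious difference, and p<0.05 in about 7%, 10–14% or 34–59% of trials against a nominal 5%. Whether any offset exists, its direction and its size are unknown from the documents.

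A reader might extend this to the trial's glycaemic result as a whole. That does not follow, because the primary A1c result does not depend on the study meters. This is an inexpensive improvement to one secondary outcome and not a threat to the main conclusion.

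**What to change.** In section 7.25:
1. State that the meter-based out-of-range comparison is supportive and that between-arm glycaemic conclusions rest on laboratory A1c.
2. Pre-specify a sensitivity analysis that rescales one arm's readings over a range of offsets, for example ±1% to ±10%. Report the offset at which the confidence interval first includes no difference. Set no fixed veto at 10%.
3. Report arm-by-time change on each participant's own study meter beside the levels. Note that the first month is already on treatment and that cancellation is incomplete with a threshold outcome.

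A regression of mean meter glucose on A1c plus arm may be shown, but only descriptively. Testing is self-chosen (section 7.9), and the Livongo arm has feedback and coach contact at high and low readings (section 7.5). The arms may therefore test at different moments, which can also produce a non-zero arm term.

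The cost is a few sentences and a few re-runs of one analysis on data already collected. The downside is that the out-of-range result may have to be reported as inconclusive. Paired readings on both meters in a subsample would address the question more directly, but they need extra data collection.

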If some of the activities would occur even if the person were not in the study, as in the case of treatment or tests performed for diagnostic purposes, clearly differentiate between those activities that will be done solely for research purposes and those that are happening as part of routine care.

Please call our office at [contact] and ask to speak to someone on the Expedited Review team if you need help differentiating between what parts are research and what parts aren't.

1. Surveys and Measurements

- All study participants may complete surveys via their personal iOS smartphone device on: study qualification (intake survey/eligibility screener discussed further in Section 10.3), diabetes status (initial diabetes survey), physical activity (iPAQ), quality of life (SF-12), vitals (attached), demographics (attached) hospitalizations and interaction with health care provider (attached), and diabetes distress (attached). Most survey data will be collected at 1, 3, and 6 months. There will also be Weekly Engagement surveys (attached) which will be two simple questions each week. At the end of the study, a Feedback survey (attached) will ask participants about their study experiences. Surveys will each have a simple description to introduce participants to the survey they are being asked to take (document attached). These surveys will be administered through the Eureka mHealth Research Platform, the study's main tool for data collection, data storage, and study management. Specific usability assessments that are native to the Livongo or iHealth platform may also be shown through the device to the participants in order to gather user feedback information.
- After qualifying and providing consent to participate in the study, participants will be referred to a convenient lab for establishing hemoglobin A1c (A1c) levels and lipid panel levels. A1c labs will be collected at months 1 (baseline), 3, and 6 (closeout). For each A1c lab, 1mL of blood will be drawn. Lipid panels (total cholesterol, LDL, HDL, and triglycerides) will be collected at months 1 (baseline) and 6 (closeout). For each lipid panel lab, 1mL of blood will be drawn.

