9.0 Sample Size and Eligibility Criteria

9.1 ENROLLMENT TARGET: How many people will you enroll:

300

If there are multiple participant groups, indicate how many people will be in each group:

Livongo Health system (experimental group) - 150
iHealth glucose meter (control/standard group) - 150

9.3 SAMPLE SIZE JUSTIFICATION: Explain how and why the number of people was chosen. For multi-site studies, this is referring to the number that will be enrolled across all sites:

- Sample size:
 - *Null Hypothesis:* There is no association between use of Livongo and change in A1c.
 - *Alternative Hypothesis:* (two-sided): The use of Livongo is associated with change in A1c.

- Effect size (t-test) = 0.5%
- Evidence:
 - A1c decreased from 7.9% to 7.5% in 3 month study of mobile phone-based data service (Kollman, et al., 2007, J Med Internet Res, 9:e36)
 - A1c decreased from 8.4% to 7.85% (adults) and 8.52 to 8.06% (children) in 6 month study using a multi-access diabetes management service (Lanzola, et al., 2007, J Diabetes Sci Technol, 1:730-7)
 - Difference in change in A1c -0.35 (intervention) vs +0.15 (control) after 12 months of using an automated diabetes management system (wireless glucose transfer) (Toscos, et al., 2012, Diabetes Care, 35:498-502)
- Standard deviation = 1% (based on the above publications)
- Standardized effect size = E/S = 0.5
- Using a two-sided t-test of 0.05 and power of 80%, n=63 participants per group

We anticipate that we will be able to recruit 300 participants (150 in each arm). Using the above parameters, the study would have 80% power to detect a minimum effect size of 0.33% (and 90% power to detect a minimum effect size of 0.38%).

9.4 * PARTICIPANT AGE RANGE: Eligible age ranges: (REQUIRED)

- 0-6 years
- 7-12 years
- 13-17 years
- 18-64 years
- 65+

9.5 * STUDY POPULATIONS: Data will be collected from or about the following types of people (check all that apply): (REQUIRED)

- Inpatients
- Outpatients
- Family members or caregivers
- Providers
- People who have a condition but who are not being seen as patients
- Healthy volunteers
- Students
- Staff of UCSF or affiliated institutions
- None of the above

9.6 * SPECIAL SUBJECT GROUPS: Check the populations that may be enrolled: (REQUIRED)

- Children / Minors
- Subjects unable to consent for themselves
- Subjects unable to consent for themselves (emergency setting)
- Subjects with diminished capacity to consent
- Subjects unable to read, speak or understand English

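### The primary model for change in A1c does not commit to baseline lab A1c, which is known before randomisation; naming it would be a free gain in precision

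*Combined protocol and SAP*

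**What the plan says.** Section 7.25 (Statistical Methods) states: "The primary outcome measure is change in A1c". For the model it says: "Methods for analyzing longitudinal data (mixed-effects linear regression models or generalized estimating equations) will be used", the aim being to "look for the effect of using Livongo on change in A1c, adjusting for possible confounding variables". No covariate is listed, and the choice between the two model classes is left open. Baseline A1c appears in that section only as an optional split, at 7.0%: "Data may also be stratified by duration of diabetes and baseline HbA1c".

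Section 7.9 (Procedures / Methods) gives the timing. On visits: "A1c labs will be collected at months 1 (baseline), 3, and 6 (closeout"). On allocation: "Once the baseline A1c value is obtained, the patient will be randomized (block randomization by diabetes type"). Baseline lab A1c is therefore a pre-randomisation measurement that every randomised participant should have.

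Section 9.3 sizes the trial on an unadjusted two-sample comparison: "Effect size (t-test) = 0.5"%, with "Standard deviation = 1% (based on the above publications"). It does not say whether that SD is of change or of A1c at one visit. It expects 150 per arm and gives minimum detectable effects of 0.33% (80% power) and 0.38% (90% power).

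**The concern.** Baseline A1c is usually the strongest available predictor of change in A1c. In a randomised trial the reason to include it is precision, not confounding, because allocation already removes systematic confounding. A plan to adjust for confounders therefore gives no rule under which baseline A1c is sure to enter the model.

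Choosing a longitudinal model does not settle the matter. Baseline can be a covariate, an outcome with arm means constrained equal, an outcome with arm means free, or merely the value subtracted to form the change. The first two forms use the baseline information fully. The other two do not, and section 7.25 does not say which is meant.

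At stake are the width of the confidence interval for the primary effect, power for effects near the 0.33% that section 9.3 quotes, and a primary model fixed in advance.

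**Working it through.** **The plan's own figures.** Inputs from section 9.3: difference 0.5, SD 1, two-sided 0.05, power 80%.

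- n per group = 2 × (1.960 + 0.842)² / 0.5² = 62.8, so 63. This matches.
- Detectable effect with 150 per arm = (1.960 + 0.842) × √(2/150) = 0.323 at 80% power, and 0.374 at 90%. Based on the t distribution they are 0.325 and 0.376. The stated 0.33 and 0.38 are these rounded up.
- Power with 150 per arm (noncentral t): 81.3% at 0.33% and 99.1% at 0.5%.

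**Longitudinal model without a stated role for baseline.** Take three visits, complete data, 150 per arm and change SD 1. With arm means free at every visit, the fitted means are the sample means. The month-6 change contrast is then the difference in mean change, with SE √(2/150) = 0.1155, the same as the t-test. With arm means constrained equal at baseline, in a model that estimates the correlation between visits, the SE is 0.1000, 0.1065 or 0.1095 at baseline to month-6 correlation ρ = 0.5, 0.7 or 0.8. The covariate model gives the same values. The results are the same under compound symmetry and under a correlation that decays with time.

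**Size of the gain.** Let ρ be that correlation and k the ratio of month-6 SD to baseline SD. Both are assumptions. In units of the baseline variance:

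- unadjusted change: 1 + k² − 2ρk
- baseline-adjusted: k²(1 − ρ²)
- difference: (1 − ρk)², which is never negative and is zero when ρk = 1

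With k = 1 the variance ratio is (1 + ρ)/2, whichever way the 1% SD is read. The interval narrows by 1 − √ratio. Power is at 0.33% with change SD 1% and 150 analysed per arm; the unadjusted value is 81.3%.

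| k | ρ | Variance ratio | Interval narrower by | Power at 0.33% |
|---|---|---|---|---|
| 1 | 0.5 | 0.750 | 13% | 90.8% |
| 1 | 0.7 | 0.850 | 8% | 87.1% |
| 1 | 0.8 | 0.900 | 5% | 85.1% |
| 1.25 | 0.5 | 0.893 | 5.5% | 85.4% |
| 1.25 | 0.7 | 0.981 | 1% | 82.0% |
| 1.25 | 0.8 | 1.000 | 0% | 81.3% |
| 0.8 | 0.5 | 0.571 | 24% | 96.5% |
| 0.8 | 0.7 | 0.628 | 21% | 94.9% |
| 0.8 | 0.8 | 0.640 | 20% | 94.5% |

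With equal SDs the 95% half-width falls from 0.227 to 0.197, 0.210 or 0.216. This equals an unadjusted analysis with 150/0.75 = 200, 150/0.85 = 176 or 150/0.90 = 167 per arm.

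If 1% is instead the SD at one visit (k = 1), power at 0.33% goes from 81.3% to 90.8% (ρ = 0.5), 95.7% to 97.9% (0.7) or 99.5% to 99.7% (0.8).

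**Check by simulation** (20,000 trials per setting, k = 1, change SD 1). Power rises from 81.5% to 90.8% at ρ = 0.5 and from 81.6% to 86.8% at ρ = 0.7. The adjusted test rejects a true null 5.2% of the time in both.

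**The case against.** The strongest reply is that the comparator is not the plan. Section 7.25 foresees an adjusted longitudinal model, and baseline A1c is an obvious candidate for it. The t-test in section 9.3 is only the sample-size approximation. This stands: the gap is a missing commitment, not an exclusion, and if the team would have included baseline A1c anyway the gain is nil. The figures above measure the gain against the less favourable reading of an open plan.

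A second reply is that the gain may be small. This also stands. Entry requires a self-reported A1c of at least 7% (section 9.7), which could compress the baseline spread and push k above 1, where the gain shrinks towards zero.

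A third is that month-3 values help when month-6 values are missing. They may, so the equality with the change-score comparison is claimed for complete data only.

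The optional split at 7.0% is a weak substitute. Given the entry criterion, most participants may fall on one side of it.

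Three stronger readings are tempting, and the documents support none of them:

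- A reader might infer that the primary comparison is biased or the trial underpowered. Randomisation protects the comparison, and power at the planned effect is 99%.
- A reader might infer an inflated type I error from picking the better of an adjusted and an unadjusted result. Section 7.25 describes no unadjusted primary analysis and nothing suggests selective reporting.
- A reader might take the blocking by type of diabetes in section 7.9 as a flaw in allocation. Sections 9.7 and 9.8 admit only type 2, so the factor has one level. Blocked allocation remains valid, and this is a matter of wording.

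**Conclusion.** The point holds as a free improvement in precision, not as a design error. Section 7.25 does not commit to baseline lab A1c in the primary model. If it is left out, or kept as an outcome with free baseline arm means, the month-6 contrast with complete data is no more precise than an unadjusted change-score comparison.

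Against that reading, adjustment narrows the interval by 5% to 13% for correlations of 0.8 to 0.5 with equal SDs, and by about 0% to 24% for SD ratios of 1.25 to 0.8. Power at 0.33% moves from 81% to 85–91%, or to 81–97% over the wider range. These power figures assume that 1% is the SD of change and that 150 per arm are analysed; section 9.3 states no allowance for dropout. The correlation and the SD ratio are assumptions throughout. The price is one degree of freedom: with equal SDs and 300 participants, adjustment would lose precision only if the correlation exceeded about 0.99.

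**What to change.** Before data are analysed by arm, add to section 7.25:

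> The primary analysis estimates the between-arm difference in change in A1c from baseline to month 6, from a longitudinal model that includes continuous baseline lab A1c as a covariate (or, if baseline is kept as an outcome, constrains arm means to be equal at baseline).

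State whether the mixed model or GEE is primary, and list any other covariates by name. Without the named visit and model class, those choices would stay open even with the covariate fixed.

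Separately, and only as wording, reconcile the blocking factor in section 7.9 with the type 2-only eligibility in sections 9.7 and 9.8 by stating the allocation scheme actually used.

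The cost is a few sentences. No participants, tests or visits are added, and the randomisation set-up does not change.
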